#### **17.1.4. COMBINED SOLICITED AND UNSOLICITED ADVERSE EVENTS**

A summary of participants with all combined solicited events (regardless of their duration; where erythema, swelling and induration are reported as any events with a diameter  $\geq 1$  mm) and unsolicited AEs will be provided. Unsolicited events will be coded by MedDRA. For clintrial.gov and EudraCT posting purposes, a summary of combined solicited and unsolicited non-SAEs will be produced by System Organ Class and according to occurrence of each event. For output combining solicited and unsolicited adverse events, all serious adverse events will be considered general events since the administration site flag is not included in the expedited adverse event CRF pages. Multiple events with the same preferred term which start on the same day are counted as only one occurrence. A further differentiation of combined AEs according to seriousness, severity, or relationship is not performed.

#### **17.1.5. COVID-19 EVENTS**

For the duration of special circumstances such as the COVID-19 pandemic, additional specific information will be summarized for the exposed set by vaccine group:

- Number of participants suspected, probable or confirmed for COVID-19 infection across diagnosis,
- Number of participants who had a COVID-19 diagnosis test and assessment performed
- Number of participants with positive, negative, or indeterminate results
- Incidence of COVID-19 reported as an adverse event or serious adverse event,
- Incidence of treatment discontinuation due to adverse event of COVID-19 infection,
- Incidence of adverse events over the time course of the trial (pre, during and post pandemic),
- Incidence of adverse by country or analysis region, age and gender over the time course of the trial (pre, during and post pandemic)

## **17.2. LABORATORY EVALUATIONS**

---

Document: C:\ProgramData\activePDF\Temp\DocConverter\API\input\99638a57dafd\$76D9DDEF7D8D4E7C  
B4DEE6C228977964.docx

Author: PPD

Version Number: Final 5.0

**CONFIDENTIAL** Version Date: 05SEP2022

A urine pregnancy test will be conducted as needed for women of childbearing potential. Pregnancy test results will be presented in a data listing.

## 18. DATA NOT SUMMARIZED OR PRESENTED

The other variables and/or domains not summarized or presented are:

- Comments

These domains and/or variables will not be summarized or presented, but will be available in the clinical study database, SDTM and/or ADaM datasets.

---

Document: C:\ProgramData\activePDF\Temp\DocConverter\API\Input\99638a57dafd\$76D9DDEF7D8D4E7C  
B4DEE6C228977964.docx

Author: PPD

Version Number: Final 5.0

**CONFIDENTIAL** Version Date: 05SEP2022

## APPENDIX 1. PROGRAMMING CONVENTIONS FOR OUTPUTS

### IQVIA Output Conventions

Outputs will be presented according to the IQVIA output conventions.

### Document Headers

All TFL is to include the following header:

GSK Vaccines Vaccine: MenABCWY Study 213171 (MenABCWY-19) - DELIVERY DESIGNATION
---

where delivery designation is the name of the current delivery, e.g., DRY-RUN, FINAL REPORT, etc.

### Dates & Times

Depending on data available, dates and times will take the form yyyy-mm-ddThh:mm:ss.

### Spelling Format

English US.

### Presentation of Vaccine Groups

For outputs, vaccine groups will be represented as follows and in the given order:

Vaccine Group	For Tables, Listings and Figures
ABCWY	ABCWY + Placebo
ACWY	ACWY + Men B

Document: C:\ProgramData\activePDF\Temp\DocConverter\API\Input\99638a57dafd\$76D9DDEF7D8D4E7C  
B4DEE6C228977964.docx

Author: PPD

Version Number: Final 5.0

**CONFIDENTIAL** Version Date: 05SEP2022

**Presentation of Visits**

For outputs, visits will be represented as follows and in that order:

Long Name (default)	Short Name
Baseline	BL
Day 1, Month 0 (Visit 1)	D1 (M0)
Day 31, Month 1 (Visit 2)	D31 (M1)
Day 181, Month 6 (Visit 3)	D181 (M6)
Day 211, Month 7 (Visit 4)	D211 (M7)
End of Study	EoS

**Tables**

The ‘Missing’ category, when appropriate, will only be presented if participants qualify for this category. Otherwise, the row for ‘Missing’ will not be presented.

**Decimal places**

Decimal places for percentages and their corresponding confidence limits will be displayed with:

Percentages and their corresponding confidence limits will be displayed with:

- no decimals when there are fewer than 50 participants in each tabulated group
- one decimal when there are at least 50 participants in at least one tabulated group
  - Exceptions will be made for percentages that are not 0% or 100% but appear as 0% or 100% due to rounding. For these specific cases the number of decimals will be increased until the displayed value is no longer 0% or 100%. Examples are given in the following table.

n/N	Displayed percentage
10/45	22%
1/45	2%
10/55	18.2%
1/55	1.8%
1/300	0.3%
1/3000	0.03%
1/30000	0.003%
299/300	99.7%
2999/3000	99.97%
29999/30000	99.997%

- The display of additional decimals for values close to 0% or 100% will be applied only to point estimates and not confidence limits, which can be rounded and displayed as 0% or 100%.
- Values of exactly 0% or 100% will be presented with no decimals regardless of the number of participants per tabulated group.
- Differences in percentages and their corresponding confidence limits will be displayed with one more decimal than the maximum number used to display the individual percentages, for example the difference between two percentages displayed with one decimal will be displayed with two decimals.

Decimal places for Demographic and baseline characteristics will be as follows:

- The mean, median, and standard deviation for continuous baseline characteristics (height, weight, body mass index (BMI), pre-vaccination body temperature) will be presented with one decimal.
- The minimum and maximum values and quartile values (if required) will be presented with the same number of decimals as the observed values.
- The maxima and minima of transformed height variables will be displayed with no decimals.
- The maxima and minima of transformed weight variables will be displayed with no decimals.

Document: C:\ProgramData\activePDF\Temp\DocConverter\API\input\99638a57dafd\$76D9DDEF7D8D4E7C B4DEE6C228977964.docx

Author: PPD

Version Number:

Final 5.0

**CONFIDENTIAL**

Version Date:

05SEP2022

- with the exception of values are below 10kg where one decimal will be displayed.
- The maximum and minima of transformed body temperatures will be displayed with one decimal.

**Serological Summary Statistics**

The number of decimals used when displaying geometric mean titers (GMT) or concentrations (GMC) and their confidence limits is shown in the following table:

GMT or GMC value	Number of decimals to display
<0.1	3
>=0.1 and <10	2
>=10 and <1000	1
>=1000	0

When multiple categories of GMT or GMC values are present in the same table, the number of decimals displayed should match that of the smallest category (i.e. the one with the higher number of decimals). For example, if GMT or GMC values of <0.1 appear in the same table as values of >=0.1 and <10, 3 decimals should be displayed for both.

GMT or GMC ratios and their confidence limits will be displayed with 2 decimals regardless of the actual values.

**Data Listings**

All data listings will be ordered by the following (unless otherwise indicated in the template):

- Randomized vaccine group (or intervention received if it's a safety output),
- Center-participant ID,
- Date (where applicable),
- For data listings where non-randomized participants would be included, these will appear in a category after the randomized vaccine groups labeled 'Not Randomized'.

Document: C:\ProgramData\activePDF\Temp\DocConverter\API\input\99638a57dafd\$76D9DDEF7D8D4E7C B4DEE6C228977964.docx

Author: PPD

Version Number: Final 5.0

**CONFIDENTIAL** Version Date: 05SEP2022

### **File Naming Convention**

The output files and corresponding SAS programs will have the same name.

The filename will start with 't', 'l' or 'f', respectively for table, listing or figure.

The filename will end with a brief description of the output content.

For output filenames (and corresponding SAS programs) that include numbers, include leading zeroes ('0') when the number is smaller than 10.

Elements in the file name will be separated by underscores '\_'.

---

Document: C:\ProgramData\activePDF\Temp\DocConverter\API\Input\99638a57dafd\$76D9DDEF7D8D4E7C  
B4DEE6C228977964.docx

Author: PPD

Version Number: Final 5.0

**CONFIDENTIAL** Version Date: 05SEP2022

## APPENDIX 2. PARTIAL DATE CONVENTIONS

Imputed dates will NOT be presented in the data listings.

When partially completed dates (i.e. with missing day or month) are used in calculations, the following standard rules will be applied:

- A missing day will be replaced by 15
- A missing day and month will be replaced by June 30th.

The following exceptions apply:

- Imputed adverse event end date occurring before the actual start date
  - If the imputed event end date occurs before the event start date then the imputed end date will be December 31st, unless this occurs after the study conclusion date in which case the earlier date is used.
- Adverse event start dates with missing day:
  - If the event starts in the same month as at least one of the study doses, the contents of AE.AESTRTPT (the flag indicating if the event occurred before or after vaccination) will be used to complete the date. If ‘after vaccination’ is selected, the imputed start date will match the first (or only) study dose given during that month. If ‘before vaccination’ is selected, the imputed date will be one day before the first (or only) study dose given during that month.
- Adverse event start dates with missing day and month:
  - If the event starts in the same year as at least one of the study doses, the contents of AE.AESTRTPT (the flag indicating if the event occurred before or after vaccination) will be used to complete the date. If ‘after vaccination’ is selected, the imputed start date will match the first (or only) study dose given during that year. If ‘before vaccination’ is selected, the imputed date will be one day before the first (or only) study dose given during that year.

---

Document: C:\ProgramData\activePDF\Temp\DocConverter\API\input\99638a57dafd\$76D9DDEF7D8D4E7C  
B4DEE6C228977964.docx

Author: PPD

Version Number:

Final 5.0

**CONFIDENTIAL**

Version Date:

05SEP2022

- Adverse event start dates with missing day and month:

All other cases of incomplete AE or concomitant medication/vaccination start date will follow the standard rules above.

---

Document: C:\ProgramData\activePDF\Temp\DocConverter\API\Input\99638a57dafd\$76D9DDEF7D8D4E7C  
B4DEE6C228977964.docx

Author: PPD

Version Number: Final 5.0

**CONFIDENTIAL** Version Date: 05SEP2022

## APPENDIX 3. PROTOCOL DEVIATIONS AND EXCLUSIONS FROM ANALYSIS SETS

Details of exclusions from each analysis sets are provided below. A complete list of participants excluded from each analysis set will be reviewed and confirmed by the sponsor prior to unblinding.

### Exclusion from Exposed Set (ES)

‘Study intervention not administered at all’, ‘Fraudulent data’ and code ‘Invalid informed consent or fraudulent data’ will be used for identifying participants excluded from ES.

### Exclusion from unsolicited and solicited safety set

#### Unsolicited safety set

‘Study intervention not administered at all’, ‘fraudulent data’, ‘invalid informed consent’ and ‘no post-dose safety data’ will be used for identifying participants excluded from the unsolicited safety set.

#### Solicited safety set

‘Study intervention not administered at all’, ‘fraudulent data’ and ‘invalid informed consent’ and ‘no post-dose solicited safety data’ will be used for identifying participants excluded from the solicited safety set.

---

Document: C:\ProgramData\activePDF\Temp\DocConverter\API\Input\99638a57dafd\$76D9DDEF7D8D4E7C  
B4DEE6C228977964.docx

Author: PPD

Version Number: Final 5.0

**CONFIDENTIAL** Version Date: 05SEP2022

**Exclusion from Full Analysis Set (FAS)**

‘Study intervention not administered at all’, missing laboratory (Immunology) assessment (missed visit, blood draw not done at visit, sample not available for testing, result not available) and ‘Fraudulent data’ will be used for identifying participants excluded from the FAS.

**Exclusion from Per-protocol analysis Set (PPS)**

A participant will be excluded from the PPS Immunogenicity analysis under the conditions presented in Table 3:

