	6A - Missed assessment* *when impacting lab samples	By visit for Day 31 and Day 211 (based on treatment administered on Day 1 and Day 181 respectively)
	6D - Out of Window assessment* *when impacting lab samples	By visit for Day 31 and Day 211 (based on treatment administered on Day 1 and Day 181 respectively)
5. Study Procedures Criteria	3A - Not withdrawn from study after developing withdrawal criteria	By visit for Day 31 and Day 211 (based on treatment administered on Day 1 and Day 181 respectively)

Document: C:\ProgramData\activePDF\Temp\DocConverter\API\Input\99638a57dafd\$76D9DDEF7D8D4E7C B4DEE6C228977964.docx

Author: PPD

Version Number: Final 5.0

**CONFIDENTIAL** Version Date: 05SEP2022

GSK Vaccines  
 PROTOCOL 213171 (MENABCWY-019)

CTMS * Categories	GSK Deviations Code/ Description	Visit (timepoints) where the exclusion is applicable
	3B – Not discontinued from study treatment	By visit for Day 31 and Day 211 (based on treatment administered on Day 1 and Day 181 respectively)
	6A - Missed assessment	By visit for Day 31 and Day 211 (based on treatment administered on Day 1 and Day 181 respectively)
	6B – Incomplete assessment	By visit for Day 31 and Day 211 (based on treatment administered on Day 1 and Day 181 respectively)
	6C – Assessment not properly performed	By visit for Day 31 and Day 211 (based on treatment administered on Day 1 and Day 181 respectively)
	6D - Out of Window assessment	By visit for Day 31 and Day 211 (based on treatment administered on Day 1 and Day 181 respectively)
	6OT - Other assessment or time point window	By visit for Day 31 and Day 211 (based on treatment administered on Day 1 and Day 181 respectively)
	7B – Study treatment administered while contraindication	By visit for Day 31 and Day 211 (based on treatment administered on Day 1 and Day 181 respectively)

Document: C:\ProgramData\activePDF\Temp\DocConverter\API\Input\99638a57dafd\$76D9DDEF7D8D4E7C  
 B4DEE6C228977964.docx

Author: PPD

Version Number: Final 5.0

**CONFIDENTIAL** Version Date: 05SEP2022

CTMS * Categories	GSK Deviations Code/ Description	Visit (timepoints) where the exclusion is applicable
	8C – Non study treatment supply procedures	By visit for Day 31 and Day 211 (based on treatment administered on Day 1 and Day 181 respectively)
	8D – eDiary procedures	By visit for Day 31 and Day 211 (based on treatment administered on Day 1 and Day 181 respectively)

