	8F – Post study treatment observation not done	By visit for Day 31 and Day 211 (based on treatment administered on Day 1 and Day 181 respectively)
	8OT - Other deviation from study procedures	By visit for Day 31 and Day 211 (based on treatment administered on Day 1 and Day 181 respectively)  Manual case-by-case review
6. Serious adverse event criteria	9B – Adverse event of special interest	By visit for Day 31 and Day 211 (based on treatment administered on Day 1 and Day 181 respectively)
	9C - Pregnancy	By visit for Day 31 and Day 211 (based on treatment administered on Day 1 and Day 181 respectively)
	9E – SAE not reported within the expected time frame	By visit for Day 31 and Day 211 (based on treatment administered on Day 1 and Day 181 respectively)
	9F – Failure to confirm causality assessment within the expected time frame	By visit for Day 31 and Day 211 (based on treatment administered on Day 1 and Day 181 respectively)

Document: C:\ProgramData\activePDF\Temp\DocConverter\API\Input\99638a57dafd\$76D9DDEF7D8D4E7C  
 B4DEE6C228977964.docx

Author: PPD

Version Number: Final 5.0

**CONFIDENTIAL** Version Date: 05SEP2022

GSK Vaccines  
 PROTOCOL 213171 (MENABCWY-019)

CTMS * Categories	GSK Deviations Code/ Description	Visit (timepoints) where the exclusion is applicable
	9OT – Other	By visit for Day 31 and Day 211 (based on treatment administered on Day 1 and Day 181 respectively)
7. Randomization Criteria	8A - Randomization procedure (subj assigned to wrong treatment, subj rand out of order)	All
	8B - Study blinding/unblinding procedures	By visit for Day 31 and Day 211** (based on treatment administered on Day 1 and Day 181 respectively).  Manual case-by-case review
8. Visit Schedule Criteria	5A – Missed visit/phone contact	By visit for Day 31 and Day 211 (based on treatment administered on Day 1 and Day 181 respectively)
	5B – Out of window visit / contact	By visit for Day 31 and Day 211 (based on treatment administered on Day 1 and Day 181 respectively)
9. Investigation Product (IP) Compliance	7A - Study treatment not administered per protocol	By visit for Day 31 and Day 211 (based on treatment administered on Day 1 and Day 181 respectively)
	7C - Wrong study treatment or assignment administered	By visit for Day 31 and Day 211 (based on treatment administered on Day 1 and Day 181 respectively)

Document: C:\ProgramData\activePDF\Temp\DocConverter\API\Input\99638a57dafd\$76D9DDEF7D8D4E7C B4DEE6C228977964.docx

Author: PPD

Version Number: Final 5.0

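### SAP Appendix 3 Table 3 excludes participants from the PPS for procedural deviations with no condition that a dose or sample was affected, and its by-visit rule for Day 1 dosing errors does not square with SAP 7.7.2

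*SAP*

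**What the plan says.** SAP 9.2 introduces Appendix 3 as the list of deviations that compromise the immunogenicity measurements and so lead to exclusion from the PPS. Appendix 3 makes the list operative: "A participant will be excluded from the PPS Immunogenicity analysis under the conditions presented in Table 3".

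These Table 3 rows are mapped by visit to Day 31 and Day 211:
- category 5: "8D – eDiary procedures" and "8F – Post study treatment observation not done", and also 8C (supply of non-study treatment);
- category 6: "9E – SAE not reported within the expected time frame" and "9F – Failure to confirm causality assessment within the expected time frame", and also 9OT (other);
- category 8: "5A – Missed visit/phone contact" and "5B – Out of window visit / contact".

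Category 11 row 8E (equipment procedures) applies to all visits. None of these rows carries a limit, although limits appear elsewhere in the table. In category 4, 6A and 6D count only "when impacting lab samples". Rows such as 1OT, category 2 7B, category 5 8OT and category 9 7OT are flagged for manual case-by-case review.

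Dosing codes 7A, 7C, 7D, 7E, 7F and 7H are also by visit: a Day 1 error removes Day 31, and a Day 181 error removes Day 211. The double-asterisk footnote, which extends an exclusion to later visits, is attached only to 4B and to 8B in category 7.

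SAP 7.7.2 lists off-protocol dosing, dosing after a temperature deviation and dosing after expiry under randomization/vaccination errors. It then says that participants with randomization errors leave the PPS, with no limit by visit.

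**The concern.** A late causality tick-box, an eDiary problem or an omitted 30-minute observation does not in itself change a titer. Applied literally, the table discards valid results after randomization for reasons unrelated to the assay, contrary to the purpose stated in SAP 9.2. For phone contacts the reader cannot tell what the rule is.

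The set matters here. Protocol 9.4.3.1 and SAP 16.1.3 name only the PPS for both families. The sensitivity analysis in SAP 16.1.4 changes the model and names no other set. The secondary A, C, W and Y analyses on the FAS (SAP 16.2.3.1) cover titers at or above LLOQ, GMTs and GMRs, but not the four-fold-rise difference. No planned analysis would therefore show whether the exclusions had influenced the non-inferiority result.

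The dosing codes raise a separate question. Family 1 reads ABCWY at Day 211 and ACWY at Day 31, so a by-visit rule filters the two arms on different doses.

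**Working it through.** **1. Family 1 under Table 3.** The time points come from SAP 2.5.1 and Protocol Table 6. (SAP 16.1.1 prints Day 31 for the second ABCWY vaccination, which does not match them.)

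| Error under 7A, 7C–7F or 7H | ACWY, read at Day 31 | ABCWY, read at Day 211 |
|---|---|---|
| Day 1 dose | removed | kept, if the Day 181 dose was correct |
| Day 181 dose | kept | removed |

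The Day 181 row is expected, because that dose cannot affect a Day 31 titer. The Day 1 row is the asymmetry. Under SAP 7.7.2, if its last paragraph is meant to cover the dosing errors it lists, the participant leaves the PPS in either arm. Code 8A (all visits) and case-by-case 7OT already catch some Day 1 errors.

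**2. The plan's power.** Inputs from Protocol 9.2 and Table 14: margin −10 points; ACWY 95%; ABCWY 95% (Family 1), 91% for A and W, and 93% for C and Y (Family 2); one-sided 0.025. Score-test approximation:

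Power = Φ[(p1 − p2 + 0.10 − 1.96·s0)/s1], with s0 from the rates restricted to the margin and s1 from the assumed rates.

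- 91% vs 95%, 542 per group: restricted rates 86.37% and 96.37%, s0 = 0.01678, s1 = 0.01545; Φ(1.754) = 96.03% (plan 96.00%).
- 93% vs 95%, 542 per group: 99.95% (plan 99.95%).
- 95% vs 95%, 225 ABCWY vs 542 ACWY: s0 = 0.02447, s1 = 0.01728; Φ(3.010) = 99.87% (plan 99.87%).

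Products of the stated powers: Family 1, 0.9987⁴ = 99.48%, as stated; Family 2, 0.96² × 0.9995² = 92.07% (stated as 91%); both, 91.59%.

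**3. Illustration of loss.** Let f be the total non-evaluable fraction. Family 2 uses N(1−f) per group. Family 1 uses 250(1−f) ABCWY (Protocol Table 11, footnote 4) against N(1−f) ACWY. N is 603 (Protocol) or 625 (SAP Table 1).

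| f | Family 1, N=603 | Family 2, N=603 | Both, N=603 | Both, N=625 |
|---|---|---|---|---|
| 10% | 99.48% | 92.2% | 91.7% | 92.8% |
| 15% | 99.12% | 90.2% | 89.4% | 90.7% |
| 20% | 98.54% | 87.7% | 86.4% | 87.9% |

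Power for both families reaches 90% at f = 13.8% (603) or 16.4% (625), which is 3.8 or 6.4 points beyond the planned 10%. The 10% row is the planned loss; the larger values of f are assumptions.

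**4. Illustration of retained Day 1 errors.** Suppose a fraction q of the Family 1 ABCWY set had a Day 1 error and responds at rate r. The ABCWY rate becomes 0.95(1−q) + rq, tested at 225 vs 542.

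| q | r | Shift (points) | Power per serogroup |
|---|---|---|---|
| 1% | 80% | −0.15 | 99.81% |
| 2% | 50% | −0.90 | 99.05% |
| 2% | 0% | −1.90 | 95.46% |
| 2% | 100% | +0.10 | 99.90% |

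The only upward shift needs r above the rate in correctly dosed participants. As a limit case at the margin (85% vs 95%) with r = 100%, the one-sided error per serogroup is 2.8% (q = 1%) to 3.2% (q = 2%), instead of 2.5%.

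**The case against.** The strongest defence is that Table 3 is a mapping of deviation codes and the detail lies in the deviation management plan, which is not in the documents. The SAP modification history says Appendix 3 was updated to match that plan, deviations are graded important or non-important (SAP 9.2), and the sponsor confirms exclusion lists before unblinding. This stands as a reason to expect less harm in practice. It does not supply a criterion: the SAP does not say that only important deviations exclude, and the limits on other rows make their absence here look deliberate.

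A reader might infer that a T1 call on day 18, one day past its 11-to-17-day window, removes a valid Day 31 titer. The documents do not establish that. Table 3 never links T1 to T5 to a sample, and 5A/5B can be read as concerning only Visits 2 and 4. The widened analysis window in SAP 3.3 covers those visits and not the calls. The supportable statement is that the rule for calls is unclear.

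A reader might also infer that Day 1 dosing errors are definitely handled unequally in Family 1. SAP 7.7.2 prevents that conclusion. Its wording is loose, because the heading and list cover vaccination errors while the exclusion sentence speaks of randomization errors, so the two sections conflict or are at best unclear.

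Finally, the 10% allowance is meant to absorb PPS exclusions, since the Protocol glossary ties evaluability to the per-protocol analysis, and 9E and 9F can arise only after an SAE or AESI. That is fair, and it is why the power figures are illustrations.

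**Conclusion.** The concern holds as a matter for clarification before unblinding. Rows 8D, 8F, 9E and 9F, and likewise 8C, 9OT and category 11 8E, exclude without any link to a dose or sample, which contradicts SAP 9.2. Rows 5A/5B leave phone contacts undefined. SAP 7.7.2 and Table 3 do not give one rule for Day 1 dosing errors.

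For the first part the size is unknown, because the documents give no deviation rates. The thresholds of 13.8% and 16.4% total loss show how much room there is; they do not predict that the trial will run short of power. Nothing in the documents shows that these rows favour either vaccine. The dosing part is small for error rates of 1–2%, and any sizeable shift works against non-inferiority. All figures rest on the Protocol's response rates, independent serogroups and 250 ABCWY samples tested at Day 211.

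**What to change.** 1. In Table 3, and in the deviation management plan so that the two stay aligned, limit 8C, 8D, 8E, 8F, 9E, 9F, 9OT, 5A and 5B to deviations that affect a study dose or an immunogenicity sample. State that a missed or late phone contact alone does not exclude.
2. Reconcile SAP 7.7.2 with Table 3, and apply one rule for Day 1 dosing errors to both arms of Family 1, for example the double-asterisk carry-forward on 7A, 7C, 7D, 7E, 7F and 7H.
3. Prespecify the four-fold-rise non-inferiority comparison for both families on the FAS as a supportive analysis.

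The cost is a text edit to two documents before unblinding, two extra tables and a few more Day 211 exclusions. If carry-forward left 220 ABCWY participants in Family 1 instead of 225, power per serogroup would be 99.84%, and global power 99.38% instead of 99.48%.
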